#### 6.2.2.4 Time to first symptomatic skeletal event (SSE)

The time to first SSE is defined as time from randomization to the occurrence of the first SSE. SSE is defined as external beam radiation therapy (EBRT) to relieve skeletal symptoms, new symptomatic pathologic bone fracture, occurrence of spinal cord compression, or tumor-related orthopedic surgical intervention.

Patients who do not reach the SSE event will be censored at their last visit (SSE assessment).

If the complete date of the assessment is not known, but the year and month are available, Day 15 of the month will be used for the calculation.

Table 12 will be used for calculating the time to first SSE. Time to first SSE = End Date – Date of Randomization +1.

**Table 12: Censoring Rules for SSE**

Situation	End Date on or prior to cut-off date	Censored
Recorded SSE event during the study	Date of the first assessment that qualified as SSE	No
Patient has no recorded SSE event at data cut-off	Date of last SSE assessment before data cut-off	Yes

Patient lost to follow-up before data cut-off	Date of last SSE assessment or randomization date, whichever comes later	Yes
---	--	-----

This endpoint is selected from the ADTTE dataset using variable PARAMCD equal to ‘SSEFS’.

A log rank test stratified by stratification factor of PSADT ( $\leq 6$  vs.  $> 6$  months) and use of osteoclast-targeted therapy (yes vs. no) at randomization will be used to compare the darolutamide treated and placebo groups.

The hazard ratio as well as its 95% CI will be presented based on fitting a Cox regression model with treatment as factor and stratified by PSADT ( $\leq 6$  vs.  $> 6$  months) and use of osteoclast-targeted therapy (yes vs. no) at randomization.

Kaplan-Meier survival curves (product-limit estimates) will be presented by treatment arm. The Kaplan-Meier estimate of the median survival time and first and third quartiles will be presented with 95% CI. Greenwood's formula will be used for the standard error of the Kaplan-Meier estimate in the calculation of these confidence limits.

The data of the second analysis of SSE will be analyzed in addition with the RPSFT and IPE methods for the same reasons as described for the analyses of OS. Only the unadjusted SSE data will be used for testing for a statistically significant treatment effect.

**Sensitivity analysis 1: SSE-free survival** will be analyzed like time to first SSE event, death will be considered as an event. See Table 13 describe censoring rules (SSE-free survival = End Date – Date of Randomization +1).

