6.3.2.2 Time to first symptomatic skeletal event (SSE)

Time to first SSE is defined as time from randomisation to the first occurrence of SSE. Date of the first SSE will be recorded.

SSE is defined as EBRT to relieve skeletal symptoms, new symptomatic pathologic bone fracture, or occurrence of spinal cord compression or tumour-related orthopaedic surgical intervention, whichever comes first.

SSE will be assessed from randomisation until the first occurrence of SSE.

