### 6.2.2.3 Time to initiation of first cytotoxic chemotherapy

The time to cytotoxic chemotherapy (CYTOC) is defined as time from randomization to the start of the first cytotoxic chemotherapy cycle. Patients who have not taken cytotoxic chemotherapy will be right censored at their last visit.

Cytotoxic chemotherapy drugs are defined with ATC code L01A, L01B, L01C, L01D and L01X. The list of all cytotoxic chemotherapy is available under Appendix 9.7.

If the complete date of the cytotoxic chemotherapy is not known, but the year and month are available, day 15 of the month will be used for the calculation.

Table 11 will be used for calculating the time to first cytotoxic chemotherapy. Time to cytotoxic chemotherapy = End Date – Date of Randomization +1.

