**Table 11: Censoring Rules for Cytotoxic Chemotherapy**

Situation	End Date on or prior to cut-off date	Censored
Recorded cytotoxic chemotherapy during the study	Date of the first assessment that qualified as cytotoxic chemotherapy	No
Death during the study before cytotoxic chemotherapy	Date of last visit at which cytotoxic chemotherapy question was collected or randomization date whatever comes later	Yes
Patient has no recorded cytotoxic chemotherapy at data cut-off	Date of last visit at which cytotoxic chemotherapy question was collected or randomization date whatever comes later	Yes

Patient lost to follow-up before data cut-off	Date of last visit at which cytotoxic chemotherapy question was collected or randomization date whatever comes later	Yes
---	--	-----

Cytotoxic chemotherapy is a specific antineoplastic therapy and therefore the CRF question “Has the patient taken any new antineoplastic therapy since previous visit?” implies the question for cytotoxic chemotherapy.

This endpoint is selected from the ADTTE dataset using variable PARAMCD equal to ‘CYTOC’.

A log rank test stratified by stratification factor of PSADT ( $\leq 6$  vs.  $> 6$  months) and use of osteoclast-targeted therapy (yes vs. no) at randomization will be used to compare the darolutamide treated and placebo groups.

The hazard ratio as well as its 95% CI will be presented based on fitting a Cox regression model with treatment as factor and stratified by PSADT ( $\leq 6$  vs.  $> 6$  months) and use of osteoclast-targeted therapy (yes vs. no) at randomization.

Kaplan-Meier survival curves (product-limit estimates) will be presented by treatment arm. The Kaplan-Meier estimate of the median survival time and first and third quartiles will be presented with 95% CI. Greenwood's formula will be used for the standard error of the Kaplan-Meier estimate in the calculation of these confidence limits.

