**Table 15: Censoring Rules for prostate cancer-related invasive procedure**

Situation	End Date on or prior to cut-off date	Censored
Recorded prostate cancer-related invasive procedure during the study	Date of the first assessment that qualified as prostate cancer-related invasive procedure	No
Death during the study before prostate cancer-related invasive procedure	Date of the last visit at which prostate cancer-related invasive procedure question was collected or randomization date whatever comes later	Yes
Patient has no recorded prostate cancer-related invasive procedure at data cut-off	Date of last visit at which prostate cancer-related invasive procedure question or randomization date whatever comes later	Yes
Patient lost to follow-up before data cut-off	Date of last visit at which prostate cancer-related invasive procedure question or at the data cut-off, whichever occurs first	Yes

This endpoint is selected from the ADTTE dataset using variable PARAMCD equal to 'CRIP'.

A log rank test stratified by same stratification factors used in the MFS analysis will be used to compare the darolutamide treated and placebo groups.

The hazard ratio as well as its 95% CI will be generated with a Cox regression model as for MFS.

Kaplan-Meier survival curves (product-limit estimates) will be presented by treatment arm. The Kaplan-Meier estimate of the median time to first prostate cancer-related invasive procedure and first and third quartiles will be presented with 95% CI.

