**Table 16: Censoring Rules for antineoplastic therapy**

Situation	End Date on or prior to cut-off date	Censored
Recorded antineoplastic therapy during the study	Date of the first assessment that qualified as antineoplastic therapy	No
Death during the study before antineoplastic therapy	Date of last visit at which antineoplastic therapy question was collected or randomization date whatever comes later	Yes
Patient has no recorded antineoplastic therapy at data cut-off	Date of last visit at which antineoplastic therapy question was collected or randomization date whatever comes later	Yes
Patient lost to follow-up before data cut-off	Date of last visit at which antineoplastic therapy question was collected or at the data cut-off, whichever occurs first	Yes

This endpoint is selected from the ADTTE dataset using variable PARAMCD equal to 'ISAT'.

A log rank test stratified by same stratification factors used in the MFS analysis will be used to compare the darolutamide treated and placebo groups.

The hazard ratio as well as its 95% CI will be generated with a Cox regression model as for MFS.

Kaplan-Meier survival curves (product-limit estimates) will be presented by treatment arm. The Kaplan-Meier estimate of the median time to initiation of subsequent antineoplastic therapy and first and third quartiles will be presented with 95% CIs.

A summary of first subsequent antineoplastic therapy will be provided.

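### SAP Tables 11, 12, 13, 15 and 16 date events by the qualifying assessment, contrary to the SAP's own endpoint definitions; event times run late, although treatment comparisons hardly move

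*SAP*

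**What the plan says.** **Definitions.** SAP 6.2.2.4: "The time to first SSE is defined as time from randomization to the occurrence of the first SSE". SAP 6.2.2.3 defines the chemotherapy endpoint as "time from randomization to the start of the first cytotoxic chemotherapy cycle". SAP 6.2.3.2 runs to the date of the procedure, and SAP 6.2.3.3 to initiation of therapy.

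**Data collected.** Protocol 6.3.2.2: "Date of the first SSE will be recorded". Protocol 6.3.2.3 records the name and start date of chemotherapy. The visit lists in Protocol 6.1.2 and 6.1.3 ask for the date of the first invasive procedure, and 6.1.3 records use of systemic antineoplastic therapies.

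**Derivation tables.** The event End Date is:
- Table 12 (and Table 13, SSE-free survival): "Date of the first assessment that qualified as SSE"
- Table 11: "Date of the first assessment that qualified as cytotoxic chemotherapy"
- Table 15: "Date of the first assessment that qualified as prostate cancer-related invasive procedure"
- Table 16: "Date of the first assessment that qualified as antineoplastic therapy"

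The SAP text states that these tables are used to calculate the times. The column heading limits every End Date to the cut-off or earlier.

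**What an assessment is.** For SSE the SAP equates it with a visit: "Patients who do not reach the SSE event will be censored at their last visit (SSE assessment". After day 29, visits and contacts are 16 weeks apart, within 7 days either way (Protocol Tables 3 and 4).

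**The concern.** An SSE or a chemotherapy start happens on a day between visits and is reported at the next one. If the reporting visit supplies the event date, the derived variable is no longer the defined endpoint: every time is lengthened by the wait until the next contact, and events pile up at visit days.

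Chemotherapy and SSE are third and fourth in the alpha-controlled hierarchy of SAP 6.2.2. Their final thresholds depend on the numbers of events actually observed, so the rule that decides which events count, and when, should leave the programmer no choice. Kaplan-Meier medians and quartiles are planned outputs. Other tables do use the event's own date (Table 19 for opioid use, Table 4 for the start of prohibited treatment), so the convention also differs within the document.

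**Working it through.** **Plan's own figure.** The documents give no number for this dating rule. Their main design figure, about 91% power for MFS with 385 events, reproduces. Freedman's formula at 2:1 and hazard ratio 0.71 gives √[385 × 2 × 0.29² / (1 + 2 × 0.71)²] − 1.96 = 3.325 − 1.96 = 1.365, or 91.4% power. This point does not affect it.

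**Size of the delay.** Input: 16 weeks = 112 days; 30.44 days per month (SAP 4.5).
- Event uniform within the interval: mean 112/2 = 56 days = 56/30.44 = 1.84 months.
- Maximum: 112 days = 3.68 months. With the visit windows at both ends, (112 + 14)/30.44 = 4.14 months.
- Simulation that includes the day 15 and day 29 visits: mean about 52 days.

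**Effect on Kaplan-Meier estimates.** The delayed curve is right at visit days and too high between them. The average excess is at most about rate × 56/365.25. At an assumed 5% per year that is 0.05 × 0.153 = 0.8 percentage points; at 20% per year, 3.1 points.

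**Effect on the comparison.** Simulation with N = 1500 at 2:1, uniform 40-month accrual and cut-off at month 52. Assumed, because the documents do not give them: 40% dropout by 36 months (they give no time scale for the 40%), placebo event rates of 3% to 20% per year, and hazard ratios of 0.5 to 0.8. Same recorded events, dated two ways:

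| Placebo rate, true HR | HR, event date | HR, visit date | z, event date | z, visit date |
|---|---|---|---|---|
| 6%, 0.65 | 0.650 | 0.652 | −2.417 | −2.416 |
| 12%, 0.65 | 0.649 | 0.653 | −3.326 | −3.321 |
| 20%, 0.50 | 0.501 | 0.508 | −6.326 | −6.307 |

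The hazard ratio moves by less than 0.01 and z by at most about 0.02.

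**Events near the cut-off.** An event that falls after a patient's last visit but before the cut-off is first reported after it. To first order the share of such events is the mean time since last visit divided by mean follow-up; the event rate cancels. With cut-off at month T from first enrolment and 40-month uniform accrual, mean follow-up is T − 20 months:

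| Cut-off | 1.84/(T − 20) | Simulation at an assumed 5% per year |
|---|---|---|
| Month 48 | 1.84/28 = 6.6% | 6.3% |
| Month 52 | 1.84/32 = 5.7% | 5.5% |
| Month 66 | 1.84/46 = 4.0% | 3.7% |

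With the dropout assumption above, month 52 gives 4.0% to 4.8%. The loss is zero if only reports made up to the cut-off enter the analysis.

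**Why the censoring rule matters.** Suppose every event dated up to the cut-off were counted while event-free patients were still censored at their last visit. Events would cover 28 months on average at month 48, but person-time only 28 − 1.84 = 26.16. A true 5.0% per year would be estimated at 5.0 × 28/26.16 = 5.35%; simulation gives 5.33%.

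**The case against.** The best defence is that the event rows are loose template wording and that everyone would programme the event date. There is support for this. No event row names a visit, while the censoring rows of Tables 11, 15 and 16 do. SAP 6.2.2.3 imputes day 15 for an incomplete chemotherapy date, which makes sense only if the therapy date is used. The same phrase appears in Table 10, where it suits a questionnaire.

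This stands in part. For chemotherapy the SAP contradicts itself rather than laying down a visit-date rule. For SSE the defence is weaker, because SAP 6.2.2.4 equates assessment with visit and imputes the date of the assessment. Either way, two programmers could build different datasets.

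It can also be said that inference is untouched. For the hazard ratio and log-rank test that is essentially right, since both arms share one schedule. Two of the four endpoints are additional ones whose p-values SAP 6.2.3 calls informative only.

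**Conclusion.** The contradiction between definitions and derivation tables is real and should be corrected. Read literally, the tables make event times about 52 to 56 days late on average, up to 112 days plus the window. That distorts Kaplan-Meier estimates and leaves the treatment comparison nearly unchanged. About 4% to 6% of events could go uncounted near a cut-off after accrual ends. This is conditional on the use of later records, and rests on assumed event rates, accrual pattern, dropout and cut-off month.

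A reader might infer more, but the documents do not support it:
- *That all four endpoints are firmly tied to visit dates.* The text settles this only for SSE; for chemotherapy it conflicts with itself.
- *That about 10% of events are lost.* This needs a cut-off near month 36, before the stated 40-month accrual ends.
- *That the SSE median is late.* At an assumed 5% per year the median would be ln 2/0.05 = 13.9 years, against a maximum study duration of 6 years, so it would not be estimable. Any shift would show in the curve.
- *That the tests are biased.* The calculations show no material change.

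**What to change.** 1. In Tables 11, 12, 13, 15 and 16, set the event End Date to the recorded date of the first SSE, the start of the first cytotoxic chemotherapy, the first procedure, or the start of the first antineoplastic therapy.
2. Use one ascertainment limit for events and censoring: count events reported at assessments on or before the cut-off, and censor event-free patients at their last such assessment.
3. If reports made after the cut-off are used to count events dated up to it, censor patients confirmed event-free at a later assessment at the cut-off, not at their last earlier visit. Otherwise the event rate is inflated as shown above.

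The cost is SAP wording and the matching derivation specification. SSE, chemotherapy and procedure dates are already collected under the protocol. For subsequent antineoplastic therapy, confirm that the start date is held in the medication dataset from which SAP Appendix 9.8 selects.

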**Table 13: Censoring Rules for SSE-free survival**

Situation	End Date on or prior to cut-off date	Censored
Recorded SSE event during the study	Date of the first assessment that qualified as SSE	No
Death during the study before SSE assessment	Date of death	No
Patient has no recorded SSE at data cut-off	Date of last SSE assessment or randomization date whichever comes later	Yes
Patient lost to follow-up before data cut-off	Date of last SSE assessment or at the data cut-off, whichever occurs first	Yes

This endpoint is selected from the ADTTE dataset using variable PARAMCD equal to ‘SASSEDTH’.

A summary description of skeletal events will be tabulated.

### 6.2.3 Tertiary or additional efficacy analysis

Calculating the p-value for tertiary endpoints has informative character only. These efficacy endpoints are:

#### 6.2.3.1 Progression-free Survival (PFS)

PFS is defined as the time (days) from the date of randomization to the date of radiological disease progression based on independent blinded central reading, including progressing pelvic lymph nodes and new pathologic lymph nodes identified above or below the aortic bifurcation or death due to any cause, whichever occurs first. The radiological progression component of PFS will be derived by taking all distant metastasis events as determined for the MFS endpoint, adding all local radiological progression events per RECIST evaluation and choosing whatever comes first, in cases where both types of radiological progression were observed.

Censoring rules for PFS are derived from the rules used for MFS as in Table 14.

#### Censoring Rules

Time of PFS is calculated as time to PFS = End Date-Date of randomization +1.

**Table 14: Censoring Rules for PFS Based on independent blinded central reading Data**

Situation	End Date on or prior to cut-off date	Censored
Documented metastasis or local progression	Date of documented metastasis	No
Documented metastasis at baseline	Date of randomization	No CCI ██████████ ██████████ I
Documented metastasis or local progression after two or more consecutively missed tumor assessments, i.e. metastasis later than last evaluable scan + (32 +1) weeks	Date of last tumor assessment that the patient was known to be metastasis-free	Yes
Death before documented metastasis or local progression and not later than last evaluable scan + (32+1) weeks	Date of death	No
Death before documented metastasis or	Date of last tumor assessment that	Yes

Situation	End Date on or prior to cut-off date	Censored
local progression and after two or more consecutively missed tumor assessments, i.e. death later than last evaluable scan + (32+1) weeks	the patient was known to be metastasis-free	
Discontinued the study before any post-baseline tumor assessments	Date of randomization	Yes
Discontinued the study before any post-baseline tumor assessments and died within (32+1) weeks after randomization	Date of death	No
Discontinued the study before any post-baseline tumor assessments and died later than (32+1) weeks after randomization	Date of randomization	Yes
Discontinued the study, but no documented metastasis or local progression	Date of last tumor assessment before discontinuation	Yes
Prohibited new anticancer treatment started prior to documented metastasis or local progression	Date of last tumor assessment before start of prohibited new treatment	Yes
Patients still on treatment without documented metastasis or local progression as of data cut-off	Date of last tumor assessment	Yes

If the complete date of the scan is not known, but the year and month are available, Day 15 of the month will be used for the calculation.

The date used for the calculation of PFS is the actual (rather than scheduled) date of assessment (i.e. actual scan date); incomplete scans are not considered unless they showed progression.

This endpoint is selected from the ADTTE dataset using variable PARAMCD equal to ‘PFS’ (baseline metastasis non-censored) and ‘SAPFSBAS’ (baseline metastasis censored).

The two treatment groups will be compared using a stratified two-sided log-rank test with an alpha of 0.05 stratified by the same stratification factors used in the MFS analysis.

The product-limit estimates of the survival distribution functions (Kaplan-Meier) will be presented for each treatment group: N, total censored, total failed, time to progression (median and its 95% CI, first and third quartiles, range), rate of patients who did not yet progressed at 4,8, 12, etc. months, KM curves.

The hazard ratio (darolutamide over placebo) and its 95% CI will be generated with the Cox model as for MFS.

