6.3.3 Additional efficacy variables

6.3.3.1 Progression-free survival

PFS is defined as time between randomisation and evidence of any radiographic disease progression, including new pathologic lymph nodes identified above or below the aortic bifurcation or death from any cause, whichever occurs first.

Status of PFS will be assessed from randomisation until the first evidence of radiographic disease progression.

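### SAP Table 14 dates a PFS event of local progression by the metastasis date, contradicting the first-event rule in section 6.2.3.1

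*SAP*

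**What the plan says.** SAP section 6.2.3.1 measures PFS from randomization "to the date of radiological disease progression based on independent blinded central reading, including progressing pelvic lymph nodes". It builds the radiological component from the MFS metastasis events, "adding all local radiological progression events per RECIST evaluation and choosing whatever comes first". Protocol section 6.3.3.1 agrees: "PFS is defined as time between randomisation and evidence of any radiographic disease progression", with nodes above or below the aortic bifurcation included.

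The same SAP section then says that its censoring rules come from the MFS rules, and gives the formula: "Time of PFS is calculated as time to PFS = End Date-Date of randomization +1". End Date is a column of Table 14. Two rows matter here:

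- **Row 1.** Situation: "Documented metastasis or local progression". End date: "Date of documented metastasis". Not censored.
- **Late progression after two or more missed assessments.** The situation names metastasis or local progression, but the explanatory clause that sets the time limit mentions metastasis only. End date: "Date of last tumor assessment that the patient was known to be metastasis-free". Censored.

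**The concern.** Row 1 admits two kinds of event and supplies a date for one of them. Because PFS time is computed from the End Date column, that cell fixes the analysis time. Read literally, it disagrees with the section's own instruction of "choosing whatever comes first, in cases where both types of radiological progression were observed".

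The likely origin is visible. Row 1 of Table 2 (MFS) has the same end date, and it is right there because local progression is not an MFS event. In Table 14 the situation column was widened and the end-date column was not.

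The patients concerned are the ones who make PFS differ from MFS. The protocol's amendment history gives capturing loco-regional progression as the reason for adding PFS (Amendment 1, Modification 3). PFS also gets a stratified log-rank test, Kaplan-Meier estimates and a hazard ratio, all of which use this date. Two programmers working independently, one from the table and one from the text, would produce different datasets.

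**Working it through.** The plan states no figure on this point, so there is none to reproduce. The check applies both rules to the same patients.

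**Can such patients occur?** Yes. Protocol sections 4.7.2.1 and 6.3.1 do not treat new or progressive regional nodes as metastasis, keep those patients on study treatment, and continue scans every 16 weeks until confirmed metastasis. Local progression followed by metastasis, and local progression alone, are both possible.

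**Does another row rescue a local-only progressor seen on schedule?** No. The death, prohibited-treatment and still-on-treatment rows, and the row for discontinuation without progression, all presuppose no earlier local progression. The remaining discontinuation rows require that no post-baseline scan was done.

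**Inputs.** Scan interval 16 weeks (Protocol 6.3.1); PFS day = end date − randomization date + 1 (SAP 6.2.3.1); 30.44 days per month (SAP 4.5). The patients are assumed examples, with scans exactly on schedule.

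A scan at week *w* falls on PFS day 7*w* + 1. Week 32 gives 7 × 32 + 1 = 225 days (225 / 30.44 = 7.4 months). Week 64 gives 7 × 64 + 1 = 449 days (449 / 30.44 = 14.8 months).

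| Assumed patient | Section 6.2.3.1 rule | Table 14 row 1, literal |
|---|---|---|
| Local week 32, metastasis week 64 | day 225 | day 449 |
| Local week 32, never metastasis | day 225 | no date |
| Metastasis week 32, local week 48 | day 225 | day 225 |
| Both on the week 32 scan | day 225 | day 225 |
| Metastasis only, week 32 | day 225 | day 225 |

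The delay equals the gap between local progression and metastasis:

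- one interval: 16 × 7 = 112 days, 112 / 30.44 = 3.7 months
- two intervals: 224 days, 7.4 months
- three intervals: 336 days, 11.0 months

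**Missed-scan row.** Assume a clean scan at week 16, weeks 32 and 48 missed, and local progression without metastasis at week 64. The limit is 16 + 33 = week 49, so the progression is late and the patient is censored. The last scan known to be metastasis-free is the week 64 scan itself (day 449). The last scan free of both kinds of progression is week 16 (7 × 16 + 1 = day 113). The literal wording censors 449 − 113 = 336 days (11.0 months) later than a progression-free rule would.

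**The case against.** The strongest reply is that the SAP already contains the right rule. Section 6.2.3.1 defines the event date, adds the local events and takes the first. The protocol agrees, and nothing says that the table overrides the text. For several other endpoints the SAP says expressly that the table is to be used for calculating the time; for PFS it introduces Table 14 only as censoring rules derived from MFS. A careful programmer would probably follow the text. This stands in part: misdating is a consequence of literal programming, not a certain outcome. It does not remove the need for correction, because the formula for PFS points to the End Date column. The note below the table, that actual rather than scheduled scan dates are used, does not say which scan is meant.

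Several stronger readings are tempting, and the documents do not support them:

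- *Every patient who progresses locally is misdated.* No: when metastasis comes first or appears on the same scan, both rules give the same date.
- *PFS collapses into MFS.* The literal date equals the MFS metastasis date for patients with local progression and then metastasis. For local-only progressors it does not: MFS does not count them as events, whereas Table 14 counts an event and gives it no date.
- *The error is at least one 16-week interval.* Not a true lower bound: visits have a ±7-day window (Protocol 6.1.2.4), unscheduled imaging is allowed for suspected progression (Protocol 6.1.4), and unscheduled visits enter the non-QoL analyses (SAP 4.5).
- *Both missed-scan rows are wrong.* The death row already requires death before any local progression, so its last metastasis-free scan is also the last progression-free scan.

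**Conclusion.** Table 14 is wrong as written in the row 1 end date, and it contradicts section 6.2.3.1 of the same SAP. The late-progression row after missed scans carries over the same metastasis-only wording.

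If the table is programmed literally, PFS is late by about 112 days for each scheduled scan interval between local progression and a later metastasis, and is undefined for patients with local progression only. These sizes rest on scans done on schedule and on assumed patients. The number of such patients is not in the documents.

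A reader might infer a biased PFS hazard ratio. The documents do not establish that: the rule is the same in both arms, and neither the number affected nor their split by arm is given. SAP section 6.2.3 makes PFS an additional endpoint whose p-value is informative only, so MFS, OS and the other secondary endpoints are untouched. This is a minor point, worth correcting because the contradiction is plain and the repair is simple.

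**What to change.** Three points of wording in Table 14:

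1. **Row 1 end date.** Use the earlier of the first documented metastasis date and the first documented local-progression date.
2. **Late progression after missed scans.** Make the time limit apply to metastasis or local progression found more than 32+1 weeks after the last evaluable scan. Censor at the last tumor assessment before the missed assessments at which the patient was known to be free of both.
3. **Death after missed scans.** No substantive change is needed. The end-date label may be harmonized for consistency.

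The cost is SAP table wording, plus a check that the derivation program for the PFS records already takes the earlier date. No new data are needed and no other endpoint changes.
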